non-responders for Δ VPeak was 0.94 [18]. While the optimal Δ VPeak varied from 7-20% among studies, one of the larger series using a Δ VPeak of 10% as a threshold found the sensitivity and specificity to be 100% in distinguishing fluid responders based on aortic velocity-time integrals identified by transthoracic echocardiogram [7]. Based on these results, we plan to define fluid responders as those who have $>10\%$ Δ VPeak between pre- and post-fluid challenge.

Bedside evaluation of the IVC to calculate the CI is a commonly used tool in adults [19, 20]. It serves as a surrogate to measure preload variation induced by mechanical ventilation. The technique requires limited ultrasonographic experience often at the critical care or anesthesia fellow level. In pediatrics, the predictive utility of IVC CI has only been evaluated in small series with conflicting results [21].

The CRI is another non-invasive devise using a photoplethysmographic probe (CipherOx-CRI) placed on the index finger. Based on data gathered from the probe, a computer-generated algorithm is then used to calculate a number between zero and one, referred to the CRI (Figure 3) [22]. The CRI correlates to one's intravascular volume status and proximity to hemodynamic collapse [23].

Figure 3

Legend: CRI, compensatory reserve index. CRI=1 is normovolemia and CRI=0 is the point at which the patient is at highest risk for hemodynamic decompensation.

Confounding factors that can influence dynamic measurements must also be considered. For instance, cardiac arrhythmias, small tidal volumes, spontaneous respiration, and high positive end-expiratory pressure have been found to decrease the predictive utility of pulse pressure variability and IVC CI [24-26]. Thus, it is paramount to use and apply these measurements in the appropriate clinical setting. Presumably, the influence confounding variables have on the predictive utility of these indices in children is similar to that of adults, however, comparative analyses have not been performed. Thus, when interpreted in the appropriate clinical context, these minimally and non-invasive devices are tools available to guide a balanced fluid resuscitation; however, while small series exist in various pediatric populations, validation is necessary in order to apply these tools in hypovolemic children with significant blood loss.

Protocol #: 18-2513

PI: [name]

Version date: 07/01/2019

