Hypothesis II: CRI and collapsibility index will reliably predict fluid responsive patients with an approximate area under the receiver operating characteristic curve (AUROC) of 0.9 while other indices will have a lower predictive accuracy.

Aim III: Evaluate confounding variables that may influence predictive measures outlined in Aim II.

Hypothesis III: Confounding variables that may decrease the predictive accuracy of indices described in Aim II include spontaneous breathing over the ventilator, minimal blood loss, and hypothermia

4. Materials and Methods:

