4.8 Data Analysis

Protocol #: 18-2513

PI: [name]

Version date: 07/01/2019

Univariate comparisons between various measures will be compared between the fluid responder and non-responder groups using t-tests or Fisher's exact test for continuous and categorical measures, respectively. Area under the curve will be calculated for CI and CRI using both simple logistic regression models including no confounders and multiple logistic regression models including confounders. Confounders will be identified for inclusion in the multiple logistic regression models by calculating the univariate association with the gold standard (using a $p < 0.10$ threshold). These adjusted models will be used to verify thresholds for classification using CI and CRI which will then be applied to calculate classification summary measures (e.g., PPV, NPV, sensitivity, and specificity). Data analysis will be performed by a biostatistician funded by the Division of Pediatric Surgery using R and SAS statistical software programs.

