Aim III: Evaluate confounding variables that may influence CRI or collapsibility index

Variable	Scale of Measurement	Data Point Location	Analysis Method
Outcome Variable IVC CI, CRI, PPV, SVV, HR, SBP, MAP AUROC	Interval	Pre-bolus measurements	
Confounding Variables Age Weight BMI Gender Ethnicity Associated syndrome Preoperative Hemoglobin Duration of NPO status Core temperature at time of bolus Paralysis provided (Y/N) Blood transfusion (Y/N) Total blood volume Total Crystalloid Total Colloid Vasopressor requirement Total amount of vasopressor Ventilation Tidal volume PEEP PIP Spontaneous breaths	Interval Interval Interval Dichotomous Ordinal Dichotomous Interval Interval Interval Dichotomous Dichotomous Interval Interval Interval Dichotomous Interval Interval Dichotomous	Demographics Demographics Demographics Demographics Demographics Demographics Demographics Preop results Anesthesia Rec Anesthesia Rec Ventilator Ventilator Ventilator Ventilator	Multivariable Linear Regression

Figure or Table will depend on results found. If neither of the outcome variables are affected by the confounding variables may only report this finding in the text.

Two separate analyses will be performed – one for the 10 ml/kg protocolized bolus provided immediately after induction and one accounting for all boluses provided.

Protocol #: 18-2513

PI: [name]

Version date: 07/01/2019

Reference:

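### Screening covariates on responder status at p<0.10 is the wrong entry test for factors that distort CI or CRI; pre-specify the Hypothesis III factors and report accuracy by factor level

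*Combined protocol and SAP*

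**What the plan says.** Section 4.8 plans unadjusted and adjusted logistic models for CI and CRI. On entry to the adjusted models it says: "Confounders will be identified for inclusion in the multiple logistic regression models by calculating the univariate association with the gold standard". The cut for entry is p<0.10. The same section compares responders with non-responders "using t-tests or Fisher's exact test for continuous and categorical measures, respectively", and I take these to be the screening tests too. On the use of the models it says: "These adjusted models will be used to verify thresholds for classification using CI and CRI". Those thresholds then give PPV, NPV, sensitivity and specificity.

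Hypothesis III (Section 3) reads: "Confounding variables that may decrease the predictive accuracy of indices described in Aim II include spontaneous breathing over the ventilator, minimal blood loss, and hypothermia". The background text before Section 3 says that arrhythmia, small tidal volume, spontaneous respiration and high PEEP "have been found to decrease the predictive utility of pulse pressure variability and IVC CI".

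Section 5, Aim III, plans a separate multivariable linear regression with the pre-bolus indices as outcome. Its covariates include spontaneous breaths and "Core temperature at time of bolus", and no p-value screen is stated for it. Nothing says that its result passes to the Section 4.8 models. Neither section plans an index-by-factor interaction or a stratified AUROC.

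**The concern.** The screen and the hypothesis concern different relations. The screen tests factor against responder status. Hypothesis III and the background describe factors that spoil what an index can tell about responder status. A factor that moves the index reading equally in responders and non-responders has no expected association with the label, so the screen should discard it. Yet such a factor makes a single cut-off behave differently from child to child.

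The stake is how the threshold check is read. If the adjusted and unadjusted results agree, the natural conclusion is that confounders do not matter. Agreement is also what one would see if the relevant factors had been screened out. A cut-off that performs poorly in cold or spontaneously breathing infants could then be carried forward with apparent support.

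**Working it through.** The plan gives no retention rate to reproduce, and the text available to me states no sample size.

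**Inputs from the plan:** p<0.10, t-test and Fisher's exact test (4.8); about half responders at the first bolus (Hypothesis Ia); AUROC about 0.9 for CRI and CI (Hypothesis II).

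**Assumptions:** two-sided tests; N=30 from the 30 probes in Section 4.2, with N=60 as a range for more events; independent observations (repeat boluses in a child are correlated, so N=60 is optimistic); 40% prevalence for a yes/no factor; the shift sizes below.

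**Step 1. Factor unrelated to response.** A t-test passes a continuous factor at its nominal rate, 10% at any N. For a yes/no factor, sum the binomial probabilities of all 2x2 tables with Fisher p<0.10:
- N=30 (15 v 15): 4.1%
- N=60 (30 v 30): 5.2%

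Across prevalences of 10-50% the range is 2.4-4.3% at N=30 and 2.6-5.6% at N=60. If one yes/no and one continuous factor are both unrelated to response, and independent of each other, both are absent in 0.959 x 0.90 = 86% of trials at N=30.

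**Step 2. Factor related to response.** The same enumeration, and the noncentral t with noncentrality d x sqrt(n/2), n per group, give the chance of entry:

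| Difference between responders and non-responders | N=30 | N=60 |
|---|---|---|
| Yes/no, 50% v 20% | 37% | 71% |
| Continuous, d=0.5 | 38% | 61% |
| Continuous, d=0.8 | 69% | 92% |
| Continuous, d=1.0 | 85% | 98.5% |

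At N=30 the 50% v 20% factor is missed in 100 - 37 = 63% of trials.

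**Step 3. What omission costs if the factor shifts the reading.** Take a binormal index with separation sqrt(2) x z(0.90) = 1.81 SD and a factor in 40% of events, unrelated to response. The AUROC without the factor is 0.875, 0.847 and 0.814 for shifts of 1, 1.5 and 2 SD. Entering the factor restores 0.90 each time.

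For a downward shift of 1.5 SD, the cut-off that maximises sensitivity plus specificity lies 0.40 SD above the unaffected non-responder mean:
- Factor absent: sensitivity Φ(1.81 - 0.40) = 0.92, specificity Φ(0.40) = 0.66.
- Factor present: sensitivity Φ(1.81 - 1.5 - 0.40) = Φ(-0.09) = about 0.47, specificity Φ(0.40 + 1.5) = 0.97.

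**Step 4. If the factor weakens the index instead.** With index noise doubled in the affected 40%, AUROC is 0.74 in them and 0.82 pooled, and still 0.82 with the factor as a main effect. With the signal halved symmetrically, it is 0.74 in them and 0.84 pooled, before and after. A main-effect covariate recovers nothing here; results by factor level, or an interaction term, would show the loss.

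**The case against.** A reader might infer that the adjusted models will nearly always omit the Hypothesis III factors. The documents do not support that. It requires every factor to act only on the index and to be unrelated to response, and Hypothesis III says only that accuracy may fall. Blood loss is among the signs used to judge fluid need (Hypothesis Ib, Section 4.5). The gold standard is itself built from variation in aortic velocity, and the background explains that such measures depend on ventilation, so spontaneous breathing could affect the label too. Step 2 shows that related factors often pass. This stands, and it makes the point conditional. It does not rescue the screen, because a low-powered test of another relation still decides whether a pre-stated factor enters.

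A reader might also infer that the covariate-to-index relation goes untested. It does not: the Section 5 regression examines it, and the plan's remark about reporting no effect of the covariates belongs to that regression. What remains is that its findings have no route into the threshold check.

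The sizes in Step 3 are illustrative, since no document gives a prevalence or a shift. The Hanley-McNeil standard error of an AUROC of 0.90 with 15 v 15 is sqrt{[0.09 + 14(0.818 - 0.81) + 14(0.853 - 0.81)]/225}, about 0.06. Losses of 0.025 and 0.053 (1 and 1.5 SD) are therefore within one standard error. They show direction and plausible scale, not a forecast.

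Finally, the background sentence concerns pulse pressure variability and IVC CI, not CRI. That temperature moves CRI is a possibility raised by Hypothesis III, not a documented fact.

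**Conclusion.** The concern holds in conditional form. Screening on responder status is the wrong entry test for a factor that distorts CI or CRI. If the factor is unrelated to response, it enters in about 4-5% of trials (yes/no, 40% prevalence, N=30-60) or about 10% (continuous). If it is moderately related, it is still often missed at N=30. Agreement between adjusted and unadjusted results would therefore not show that confounders are unimportant.

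The yes/no rates assume that the screen uses Fisher's test; with a univariate logistic test they would be nearer the nominal 10%. All rates assume about half responders and independent events. I would class this as a cheap improvement, not a flaw that invalidates the analysis.

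**What to change.** In Section 4.8, replace the p<0.10 screen with wording such as: the adjusted CI and CRI models include spontaneous breathing (yes/no) and core temperature at the bolus whatever their p-values; a factor is omitted only if it does not vary in the bolus set analysed (protocolized bolus, or all boluses). Treat the other Aim III covariates as descriptive.

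Because Hypothesis III concerns reduced accuracy, add that AUROC, and sensitivity and specificity at the chosen cut-off, will be reported by level of each factor, or through an index-by-factor interaction, labelled exploratory. Fix any grouping of temperature before analysis, or keep it continuous in the interaction.

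State that minimal blood loss is left out because blood loss as such is not in the Section 5 covariate list, and surgical loss cannot vary at the bolus given before incision.

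The cost is wording only, since both variables are already listed for collection. Two degrees of freedom are always spent: with 15 events in the smaller outcome group, an index plus two covariates leaves 15/3 = 5 per coefficient, so interactions belong in separate exploratory models. A covariate that the screen would have found can no longer enter, and estimates within levels will be imprecise.

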While numerous tools are available to guide resuscitation, one potential benefit of this project is to validate the use of CipherOx-CRI in this cohort. If CRI proves to be a valuable predictor of intravascular volume status and the need for volume expansion, this could negate the need for arterial line placement which is time consuming, invasive, and associated with complications such as arterial thrombosis. Furthermore, after validation in this cohort, additional studies could be performed in other groups of children at risk for hemorrhagic shock in the hopes to guide ongoing resuscitation accurately without the need for invasive devices.

3. Specific Aims and Hypotheses:

Aim I: Among infants undergoing cranial vault reconstruction for craniosynostosis, we aim to determine the proportion who respond to clinically administered fluid or blood products defined by pre- and post-fluid challenge $\Delta V_{Peak} > 10\%$.

Hypothesis Ia: We hypothesize that approximately half of the cohort will be fluid responsive defined by ΔV_{Peak} by $> 10\%$ after a 10 mL/kg fluid bolus is administered immediately following induction. Although this is a prediction, it is based on previous published reports suggesting a relatively even distribution among patients who clinicians believe need volume expansion. Additionally, because these children have a mean weight of 6.4 kg and will have been nil per os for several hours prior to surgery, they are at risk for intravascular volume depletion even prior to blood loss.

Hypothesis Ib: Because clinicians use pulse pressure variability, heart rate, systolic blood pressure, urine output, and blood loss to gauge need for ongoing resuscitation (either crystalloid, colloid, or blood), we suspect that more than half of subsequent fluid challenges will be given to infants who are fluid responsive (defined by a pre- and post-bolus ΔV_{Peak} of $> 10\%$).

Aim II: To determine the PPV, NPV, sensitivity, specificity, and optimal threshold for CRI, collapsibility index, pulse pressure variability, stroke volume variability, heart rate, systolic blood pressure, and mean arterial pressure as tools to predict fluid responsiveness using pre- and post-fluid challenge $\Delta V_{Peak} > 10\%$ to define fluid responders.

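### The covariate-adjusted AUC in 4.8 is screened and scored on the same outcome without optimism correction, and the same models are used to 'verify' the CI and CRI thresholds.

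*Combined protocol and SAP*

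**What the plan says.** Section 4.8 calculates the AUC for CI and CRI "using both simple logistic regression models including no confounders and multiple logistic regression models including confounders". On covariates it says: "Confounders will be identified for inclusion in the multiple logistic regression models by calculating the univariate association with the gold standard", with p<0.10 as the entry level. It then states: "These adjusted models will be used to verify thresholds for classification using CI and CRI". Those thresholds produce PPV, NPV, sensitivity and specificity. The text reviewed describes no cross-validation, bootstrap or other optimism correction, and no verification procedure.

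Hypothesis II (Section 3) expects CRI and CI to have an "approximate area under the receiver operating characteristic curve (AUROC) of 0.9 while other indices will have a lower predictive accuracy"; it does not name a model. Aim II asks for the accuracy measures and an "optimal threshold for CRI, collapsibility index, pulse pressure variability, stroke volume variability, heart rate, systolic blood pressure, and mean arterial pressure". In Section 5, the 2x2 tables classify on one cut-off per index. A value of 15% is printed for CI and none for CRI. Mock-up Table 2 has one AUC column for seven indices, not labelled adjusted or unadjusted. Influence of covariates is a separate question: Hypothesis III concerns "Confounding variables that may decrease the predictive accuracy of indices described in Aim II".

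**The concern.** Aim II asks how well a single reading, such as CRI, separates responders from non-responders. The index-only AUC answers that, and it is already planned. The adjusted AUC answers a different question, namely how well the index and a set of selected covariates do together. Because covariates enter for their association with the very outcome on which the model is then scored, chance associations count as discrimination.

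The adjusted models are also the only ones that 4.8 carries forward to the thresholds, so they are not plainly a side analysis. At stake are the accuracy figures for two devices that the background section hopes could replace arterial lines.

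**Working it through.** The text reviewed gives no sample size, power or error rate for the AUC, so there is no planned figure to reproduce.

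**Inputs**
- Responder share one half: Hypothesis Ia expects that "approximately half of the cohort will be fluid responsive".
- n=30, an assumption taken from the probe count in 4.2. n=60 is the alternative, from the 50–70 cases a year in the background section.
- 11–15 candidate covariates, an assumption. Section 4.8 names none; the Aim III table in Section 5 lists about 20, but for a different analysis.
- All candidates unrelated to response, and one bolus per child (assumptions).

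**Step 1: what the screen lets through.** For K independent null candidates tested at exactly 0.10, expected passes = 0.10K and P(at least one) = 1 − 0.9^K.
- K=11: 1.1 expected; 1 − 0.9^11 = 0.69.
- K=15: 1.5 expected; 1 − 0.9^15 = 0.79.

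Fisher's exact test is conservative, so sets with binary candidates pass somewhat fewer: 0.9 on average for 7 continuous + 4 binary, and 1.1 for 9 + 6, at n=30.

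**Step 2: effect on the AUC.** Simulation of 2,000–4,000 trials per setting. The index is normal in each group with separation d = √2·Φ⁻¹(AUC), which is 1.19 SD for 0.80 and 1.81 SD for 0.90. Candidates are screened by t-test or Fisher's test at p<0.10, a logistic model is fitted to the index plus those selected, and the AUC is taken on the same data. Ranges cover four candidate sets (7+4, 9+6, 11 continuous, 15 continuous).

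| n | True index AUC | Mean adjusted AUC | Inflation |
|---|---|---|---|
| 30 | 0.70 | 0.774–0.810 | 0.074–0.110 |
| 30 | 0.80 | 0.843–0.867 | 0.043–0.067 |
| 30 | 0.90 | 0.922–0.933 | 0.022–0.033 |
| 60 | 0.80 | 0.822–0.835 | 0.022–0.035 |
| 60 | 0.90 | 0.911–0.915 | 0.011–0.015 |

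The index-only AUC is essentially unbiased in these settings. A separate simulation with normal candidates agrees. At n=30 and true 0.80, the adjusted mean is 0.857 with 12 candidates and 0.888 with 20, against about 0.80 for the index alone. With 20 candidates, n=30 and true 0.90 it is 0.943, an inflation of 0.04.

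**Step 3: does a bootstrap repair it?** The screen is repeated in every resample (n=30, 9+6 candidates, 60 resamples, about 400 trials).
- True 0.80: apparent 0.856, corrected 0.746, actual value in new children 0.738.
- True 0.90: apparent 0.925, corrected 0.858, actual value in new children 0.866.

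The correction recovers the adjusted model's real performance. In this all-null case that performance is below the index alone.

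**Step 4: thresholds.** The adjusted model is logit(p) = b0 + b1·X + Σ gj·Zj, with X the index and Zj the covariates. A cut-off p = c corresponds to X* = (logit(c) − b0 − Σ gj·Zj)/b1. So X* moves by −gj/b1 per unit of Zj, and a single X* exists only if every gj is zero. At n=30, 51–81% of trials select at least one null continuous covariate. In those trials the largest shift has a median of 0.76–0.85 index SD per covariate SD at index AUC 0.80, and 0.52–0.60 at 0.90. At n=60 the medians are 0.50–0.55 and 0.34–0.38. This step applies only if the cut-off is placed on the predicted probability.

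**The case against.** Four stronger readings are tempting, and the documents do not support them.

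1. *Hypothesis II will be judged on the adjusted AUC.* Nothing says so. Mock-up Table 2 gives seven indices one AUC each beside a bivariate correlation, and adjusted models are planned only for CI and CRI. A like-for-like column is therefore naturally index-only. What stands is that 4.8 does not say this.
2. *Inflation lets a weaker index pass 0.9, or outrank the other indices.* Hypothesis II gives an approximate value, with no null, error rate or success rule. No section plans to set an adjusted AUC for CI or CRI against unadjusted ones for the rest.
3. *The thresholds will sit on predicted probabilities.* The sentence speaks of classification by CI and CRI, and 'verify' may mean checking an existing value such as the printed 15%. This reading is at least as likely. But no procedure is given, and CRI has no printed value to check.
4. *Adjusted models do worse than the index in new children.* This holds only when every covariate is null. With two covariates that truly differ by 0.8 SD between groups (an assumption) and an index AUC of 0.80, the adjusted model reaches 0.807 (n=30) and 0.848 (n=60) in new patients. The apparent values are still too high, at 0.916 and 0.903, and still describe index plus covariates.

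On size, the objection also has force. At a true 0.90 with 15 children per group, the Hanley–McNeil standard error of the index-only AUC is √(0.8013/225) = 0.060, so a bias of 0.02–0.03 is about half of it or less. In the all-bolus analysis there are more events: 90 independent events (9+6 candidates, true 0.80) give a mean of 0.821. Repeat boluses in one child are not independent, so the inflation would be somewhat larger than that.

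**Conclusion.** The point holds in this form: the adjusted AUC, as specified, is biased upward and is not a property of the index. The direction follows from the screening rule. The size does not come from the plan; it rests on the assumed n, candidate count, null covariates and single bolus. Under those assumptions the inflation is about 0.04–0.07 at n=30 and 0.02–0.04 at n=60 for a true AUC of 0.80. It is small at the hypothesised 0.90 and matters most if the index is weaker than hoped. It bears on Hypothesis II only if the adjusted value is presented as the index's own.

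The threshold problem is conditional on what 'verify' means. Under the predicted-probability meaning, the output cannot fill the Section 5 2x2 tables; under the checking meaning, a procedure is missing.

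**What to change.** Amend 4.8 as follows.
- Name the index-only AUC, with a 95% confidence interval, as the measure for Hypothesis II and Mock-up Table 2, for all seven indices.
- Set thresholds and compute sensitivity, specificity, PPV and NPV on the raw index. Report CI at the printed 15% cut-off and at any data-derived cut-off.
- Do not set thresholds from the adjusted models. If a check of a raw cut-off is intended, define it.
- Label any adjusted AUC as index plus covariates, and report it with a bootstrap optimism correction that repeats the p<0.10 screen in each resample. In the all-bolus analysis, resample by child.

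The cost is SAP wording, short bootstrap code and a little more analysis time. No new data are needed. The adjusted AUC may come out less favourable.
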